10.5 Concomitant Medications

Concomitant medications will be coded by WHO Drug Global B3 March 1, 2020 coding dictionary. Data will be summarized by Anatomical Therapeutic Chemical (ATC) system Level 2, Level 4, and drug preferred name. The summary tables will show the number and percentage of subjects taking each medication by ATC Level 2, Level 4, and preferred name.

For the summaries of prior and concomitant medications, subjects who take the same medication (in terms of the ATC Level 2, Level 4, and preferred name) more than once will only be counted once for that medication.

In the summary tables, prior medication and concomitant medications will be presented by sorting alphabetically.

10.6 Medical History

Medical history will be summarized by system organ class (SOC) and preferred term (PT) in descending frequency using MedDRA. In the summary tables, subjects may have had data collected under multiple system organ class (SOC) and preferred terms (PT), but for each SOC and PT category, subjects are only counted once.

10.7 Study Drug Administration and Exposure

Study drug administration will be summarized the following ways:

- Total time taken and total amount of IP administered (mL).
- Total Dose (M cells): $1.5 \times$ Total amount of IP (mL).
- Treatment duration defined as: (Date of the end of study participation (EOS dataset) – Date of first dose administration of study drug).
- Maximum infusion rate.
- Dose interruptions.

These exposure parameters will be summarized using descriptive statistics (i.e., continuous variables (by the mean, standard deviation, median, minimum and maximum values) and categorical variables (by the number and percentage of subjects in each category).

11. EFFICACY ANALYSIS

The modified Intent-to-Treat Population (as Treated) is defined as all enrolled and randomized subjects who received any amount of study treatment; the mITT population will be utilized for all efficacy analyses. All summary tables will be displayed by treatment arm.

This is a Phase 2 proof of concept study, so a hierarchical testing order will be specified, but p-values will be utilized for descriptive purposes even if a step in the hierarchy is not met and there will be no adjustment for multiplicity of analyses. In addition to the analysis by severity of COVID risk at baseline, additional subgroup analyses will be conducted on an ad-hoc basis and will be fully described in the clinical study report.

The primary analysis for each efficacy endpoint will be as follows, unless otherwise noted in the corresponding section. A Cox Proportional Hazards (PH) model will be utilized to characterize overall survival or time-to-event, correcting for baseline COVID severity risk score. This risk score will be calculated based on historical data and will include baseline characteristics of age, weight, sex, and presence of comorbidities. In addition, unadjusted Kaplan-Meier curves will be presented by treatment group and summary statistics will include estimates of median survival (and corresponding 95% confidence interval), minimum and maximum time, and the number of censored subjects. The overall survival time will be compared between the treatment arms using a log-rank test.

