## 1.2 Schema

### 1.3 Schedule of Activities

PROCEDURE / EVENT	SCREENING  Visit	TREATMENT PHASE 	FOLLOW-UP PHASE 								EVENT DRIVEN 
			Day 2	Day 3	Day 7 (± 1 day)	Day 15 (± 1 day)	Day 30 (± 3 days)	Day 60 (± 3 days)	Day 90 (± 7 days)		
Day	–5 to –1	Day 1 (IP Administration)									
Informed Consent	X										
Eligibility Assessment	X	X 									
Demographics	X										
Medical History	X										
Physical Examination	X	X 			X 	X 					
Vital Signs	X	X 	X	X	X 	X 	X 	X 	X 		
Respiratory / Ventilator Status 	X	X 	X	X	X 	X 	X 	X 	X 		
12-Lead ECG	X	X 			X 	X 	X 	X 	X 		
Pregnancy Test 	X										
Clinical Laboratory Testing 	X	X 	X	X	X 	X 	X 				
Blood Sampling for Proteomics 	X	X 	X	X	X 	X 	X 				
SARS-CoV-2 Testing	X										
Chest X-Ray	X				X 						
Ordinal Scale for Clinical Improvement	X	X 	X	X	X	X	X	X	X		
Randomization 	X										
Order Investigational Product 	X										

PROCEDURE / EVENT	SCREENING 	TREATMENT PHASE 	FOLLOW-UP PHASE 								EVENT DRIVEN 
			Visit	Day 2	Day 3	Day 7 (± 1 day)	Day 15 (± 1 day)	Day 30 (± 3 days)	Day 60 (± 3 days)	Day 90 (± 7 days)	
Day	-5 to -1	Day 1 (IP Administration)									
Administration of Investigational Product 		X									
Peripheral Venous Access Site Monitoring 		X									
Concomitant Therapies	X	X	X	X	X	X	X	X	X	X	
Adverse Events 	X	X	X	X	X	X	X	X	X	X	
Collection of Outcome Data 		X	X	X	X	X	X	X	X	X	

 Clinical laboratory conducted as part of standard of care within 7 days prior to protocol consent during index hospitalization may be used for screening visit assessments and eligibility determination.

 Eligible subjects will receive 1 dose of IP.

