 Follow-up phase will be conducted on Days 2, 3, 7 (± 1 day), 15 (± 1 day), 30 (± 3 days), 60 (± 3 days) and 90 (± 7 days). Follow-up will either be conducted in the inpatient setting or as a phone follow-up should the subject be discharged. Note that as long as the subject remains hospitalized on study the safety of the subject will be monitored on a daily basis per standard of care.

 Data that will collected on a subject-by-subject basis based on occurrence during study participation.

 Prior to baseline assessments on Day 1, Investigator is required to confirm the subject's eligibility based on the inclusion and exclusion criteria in [Section 5.1](#) and [Section 5.2](#).

 Assessment to occur prior to infusion on Day 1.

 Assessment will be conducted in the inpatient setting only if the subject is still hospitalized for this visit.

 Every 15 minutes from pre-infusion through 2 hours post-infusion.

 To capture type of ventilator and respiratory support (e.g., endotracheal ventilator, nasal O2 cannula, face mask, or ECMO) and twice daily SpO2 (%), FiO2 (%) and respiration rate (bpm).

 On treatment day, include immediately pre- and post-infusion.

 Only to be conducted for women of childbearing potential.

 Includes the following clinical laboratory samples: CBC, CMP, CRP, cytokine assay (IL-1, IL-6, TNF- $\alpha$ , INF- $\gamma$ , IL-10), troponin I, myoglobin, ferritin, and procalcitonin.

 Blood samples will be taken and submitted to a central laboratory for future proteomic assay assessment. Information on the assay and procedures for collection and shipping are located in the laboratory manual.

 Subjects will be randomized approximately 1 to 5 days prior to the planned infusion in Treatment Phase to allow enough time for IP ordering and delivery.

-  IP will be ordered approximately 1 to 5 days prior to the infusion (Day 1) in Treatment Phase to allow for enough time for IP delivery. Please see the IP Manual for ordering instructions and timelines.
-  Subjects will be observed for at least 2 hours post-infusion, including vital signs assessments every 15 minutes. The clinical site will observe local institutional policies related to parenteral infusions and post-infusion monitoring. A site Investigator will assess the subject for AEs.

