11.2 Ordinal Scale of Clinical Improvement

Since there are 9 categories of the WHO Ordinal Scale of Clinical Improvement and these categories are ordinal in nature (higher score correlates to a higher severity level) it is possible to analyze this endpoint as a continuous scale variable.

The mean change in the WHO Ordinal Scale of Clinical Improvement at each timepoint will be compared between treatment groups using a mixed model with repeated measures (MMRM), with baseline score and weighted COVID severity risk score as covariates. Due to the small sample size and unknown variances for the two independent treatment groups, a test for equal variances and normality will be applied prior to choosing the inferential

statistical method to employ. If the test for equal variances and normality is > 0.10 (indicating that the variances are not significantly different and the data is close to normally distributed) the parametric MMRM will be used to test for treatment group differences. If the test for equal variances or normality is ≤ 0.10 (indicating that the variances are significantly different, or the data is non-normally distributed) then a non-parametric MMRM will be used.

The model will test the null hypothesis that the differences in least-square (LS) means between the active and placebo groups over 90 days is equal to zero. LS means will be estimated at each visit along with treatment differences, p-values, 95% confidence intervals for the difference in LS means, and an effect size based upon Cohen's D will be provided for treatment comparisons.

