11.3 Time to Clinical Improvement on the Ordinal Scale of Improvement

Time to a clinical improvement (days) will be defined as an improvement in the WHO Ordinal Scale of Clinical Improvement of at least one category (i.e., a 1-point improvement, decrease) from baseline. For example, a 6 at baseline to 5 would constitute an improvement.

Subjects that achieve a clinical improvement will be summarized by number and percentage and analyzed for treatment group differences by use of Barnard's test.

For subjects that did reach a clinical improvement, the time taken to reach a clinical improvement will be analyzed with a Cox PH model with descriptive statistics provided by a Kaplan-Meier analysis, including median time to event, and log-rank test as described above.

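### The Cox models name only a demographic and comorbidity risk score as covariate, although the pre-infusion ordinal score is collected and already sits in the MMRM

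*SAP*

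**What the plan says.** SAP Section 11 gives a default that covers all efficacy endpoints: "The primary analysis for each efficacy endpoint will be as follows, unless otherwise noted in the corresponding section". For time-to-event outcomes the default is: "A Cox Proportional Hazards (PH) model will be utilized to characterize overall survival or time-to-event, correcting for baseline COVID severity risk score". The score is described in one sentence: "This risk score will be calculated based on historical data and will include baseline characteristics of age, weight, sex, and presence of comorbidities". No formula or weights are given.

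SAP 11.3 (time to a 1-point improvement) points back to this model: "the time taken to reach a clinical improvement will be analyzed with a Cox PH model with descriptive statistics provided by a Kaplan-Meier analysis". It adds no covariate. Neither do SAP 11.1 and 11.5 to 11.9 (mortality, respiratory support, ICU, hospital). SAP 9.2, on strata and covariates, says the topic does not apply.

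SAP 11.2 specifies the MMRM for the ordinal scale "with baseline score and weighted COVID severity risk score as covariates", that is, as two separate terms.

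In the Protocol 1.3 schedule, the row "Ordinal Scale for Clinical Improvement" is marked at Screening and on Day 1, and the Day 1 mark carries footnote 6: "Assessment to occur prior to infusion on Day 1". SAP 8.6 takes the latest pre-dose value as baseline.

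Protocol 6.3.1 and SAP 5 describe 1:1 randomisation and mention no stratification factor. SAP 4 plans up to 60 treated subjects, about 30 per arm, with no formal sample size calculation.

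**The concern.** The covariate is called a severity score, but the items named are patient characteristics that exist before the illness. Two subjects of the same age, weight, sex and comorbidity could start treatment in quite different respiratory states and be treated as equivalent by the Cox model. Protocol 5.1 and 5.2 admit subjects with low oxygen saturation or COVID-19 cardiomyopathy and exclude those who have been intubated, and Protocol 6.4 gives the product to inpatients. The possible entry scores are therefore 3 (no oxygen), 4 (mask or prongs) and 5 (non-invasive ventilation or high flow).

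The gap shows most clearly in SAP 11.3, where the event is a drop from the subject's own starting point on this scale and the model does not condition on that starting point.

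The plan claims no power and relies on its estimates to guide later studies. Precision and protection from chance imbalance are therefore what is at stake.

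**Working it through.** The plan states no power, effect size or event count, so there is no figure of its own to reproduce. The check has a text part and an illustrative part.

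**1. Text.** SAP 11.2 lists the baseline ordinal score and the risk score as separate covariates, so the plan does not treat the risk score as already containing the ordinal score. The Cox sections list the risk score alone.

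**2. Chance imbalance.** Inputs: 30 per arm (SAP 4). Assumptions: simple allocation, and a share p of subjects at score 5. With X and Y independent Binomial(30, p), the probability that |X − Y| is 5 or more is:
- p = 0.5: 24.5%
- p = 0.3: 20.4%

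**3. Scale.** By Schoenfeld's formula, power = Φ(|ln HR| × √(D/4) − 1.96), where D is the number of events.
- D = 50, HR 2.0: 0.693 × √12.5 − 1.96 = 0.49, so 68.8%.
- D = 20, HR 0.5: 0.693 × √5 − 1.96 = −0.41, so 34.1%.

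**4. Power with and without the ordinal term.** Simulation of about 3,000 trials per scenario, 60 subjects, two-sided 5% Wald test, exponential times. Both models contain treatment and a risk score with an assumed log HR of 0.3 per SD. Half of the subjects are assumed to be at score 5 and half lower. The discharge type has a base rate of 0.12 per day, censored at Day 30. The death type has a base rate of 0.003 per day, censored at Day 90.

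| Endpoint, true HR | HR of score 5 vs lower | Mean events | Median HR without / with | Power without / with | Gain (points) |
|---|---|---|---|---|---|
| Discharge, 2.0 | 1 (none) | 58.8 | 2.04 / 2.06 | 73.1% / 73.4% | 0.3 |
| Discharge, 2.0 | 0.5 | 56.2 | 1.90 / 2.03 | 63.2% / 70.0% | 6.8 |
| Discharge, 2.0 | 0.33 | 53.2 | 1.81 / 2.07 | 55.0% / 69.0% | 14.0 |
| Discharge, 2.0 | 0.25 | 50.7 | 1.74 / 2.06 | 48.1% / 66.6% | 18.5 |
| Death, 0.5 | 1 (none) | 11.4 | 0.49 / 0.48 | 14.5% / 14.9% | 0.4 |
| Death, 0.5 | 2 | 15.5 | 0.50 / 0.49 | 22.4% / 24.0% | 1.6 |
| Death, 0.5 | 3 | 19.1 | 0.51 / 0.49 | 26.4% / 29.5% | 3.1 |
| Death, 0.5 | 4 | 21.9 | 0.52 / 0.49 | 28.8% / 33.8% | 5.0 |

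The 0.33 and 0.25 rows assume a contrast stronger than a factor of 2, so they mark an upper end.

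**5. Baseline mix.** These runs used three score levels, kept the risk score in both models, and assumed a factor of 1.5 to 2 per point. The discharge-type gain was about 5 to 10 points with 15/45/40% at scores 3/4/5. It was 1 to 6 points with a narrower mix such as 5/15/80%.

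**6. No treatment effect.** Over all null trials in the step 4 set-up, the rejection rate was 3.8% to 5.8% without the term and 4.5% to 6.2% with it. The Monte Carlo standard error is √(0.05 × 0.95 / 3000) = 0.4 points. The larger model's Wald test is therefore slightly liberal in places, and a little of the gain in step 4 reflects that.

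In null trials where the active arm had at least 5 more score-5 subjects, the model without the term gave these median HRs against a true 1.0:
- discharge: 0.90, 0.81 and 0.78 (prognostic HR 0.5, 0.33, 0.25)
- death: 1.08, 1.26 and 1.30 (prognostic HR 2, 3, 4)

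**The case against.** **The MMRM contrast is ordinary practice.** Adjusting a change-from-baseline model for its own baseline is routine. It does not show that the authors judged the ordinal score a general prognostic factor and then forgot it. This stands. The contrast shows only that the score is available and distinct from the risk score.

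**The component list may not be closed.** SAP 11 says the score "will include baseline characteristics of age, weight, sex, and presence of comorbidities" and gives no formula. A reader might infer that it certainly holds no respiratory measure; the text supports only that none is named.

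**Stratification.** A reader might conclude that the trial is unstratified. Randomisation details sit in a Manual of Procedures and a Randomization Plan that are not available here, so the supportable statement is that no stratification is described.

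**Prognostic strength.** It is tempting to call the ordinal score the strongest predictor of outcome. Nothing in the documents establishes that. For time to improvement even the direction is open: a subject at 3 must become ambulatory to improve, while a subject at 5 need only step down to mask or prongs.

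**Narrow baseline range.** Protocol 6.6 says all patients will be managed in an ICU, and intubated patients are excluded. Most subjects could then share one score, and the gain falls towards the lower end of the range.

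**Exploratory status.** P-values are descriptive, and Protocol 9.4.9 already permits multivariable analyses. This limits the consequences, but a permitted analysis is not a prespecified one.

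**Conclusion.** The point holds as one of efficiency and robustness. The plan contains no error of arithmetic and no contradiction here.

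If the baseline score is prognostic, its omission costs roughly 1 to 10 points of power for discharge-type or improvement-type endpoints and about 1 to 5 for mortality. If it is not, including it costs nothing material. The discharge range rests on 30 per arm, a true HR of 2.0 and an assumed factor of 1.5 to 2 per score point. The mortality range uses a true HR of 0.5 and the step 4 contrasts of 2 to 4. The improvement figure also assumes that all subjects are followed with censoring, whereas SAP 11.3 speaks of those who did improve.

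A reader might take the shrinkage from 2.0 to about 1.8 or 1.9 as plain bias. Part of it is non-collapsibility: the model without the score estimates a hazard ratio averaged over baseline states, a different quantity from the conditional one. A reader might also infer inflated false-positive rates; the null simulations show none from the omission. What remains is lost power, a less specific estimate, and exposure to an imbalance that has a 20% to 25% chance of reaching 5 subjects under simple allocation.

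**What to change.** State in SAP Section 11, before unblinding, that the Day 1 pre-infusion ordinal score enters each Cox model as a covariate beside the risk score. A single linear term spends one degree of freedom. The priority is time to improvement, ICU discharge and hospital discharge.

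Include it for mortality too, and note there that the gain is small and that deaths limit the number of terms. With 15.5 to 21.9 deaths, as in the prognostic scenarios above, and three terms, there are about 5 to 7 deaths per term (15.5/3 = 5.2; 21.9/3 = 7.3). Report the hazard ratio as conditional on baseline status and keep the planned unadjusted Kaplan-Meier and log-rank results beside it. If the sponsor prefers to omit the score, the SAP should give the reason.

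In the same edit, list the risk score's components and weights in full, so that it is clear whether respiratory status is in it, and align SAP 9.2 with the covariates used in Sections 11 and 11.2.

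The cost is one or two SAP sentences. No new data are needed, and SAP Section 9 says the blind is intact, so the change can still be prespecified.

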11.1 All-Cause Mortality

Survival will be measured as the time (days) between the date of the start of treatment and the date of death. For subjects not known to be deceased at time of analysis, the time between date of start of treatment and date of last contact or date lost to follow-up will be calculated and used as a censored observation in the analysis. If this date is after the data cut-off, subjects will be censored at the date of data cut-off. The final cutoff for the survival analysis will be as long as possible, and a calendar date for cutoff will be determined prior to final unblinding of the study.

The Death Report (dataset: DR) will be utilized to capture the survival information (date of death).

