### **8.3.4 Time Period and Frequency for Event Assessment and Follow-Up**

All AEs will be reported from the signing of the ICF and are followed by the clinical site until an outcome is known or the subject's participation in the protocol concludes at either the Day 90 or early termination, whichever occurs first.

The clinical site is expected to review all ongoing AEs at each visit. AEs are followed until resolution or until no further changes in the event are expected (i.e., the point at which a subject experiencing an AE is treated successfully and stabilized even though he or she may continue to experience lingering sequelae that may never resolve), or it is agreed that further follow-up of the event is not warranted (e.g., non-serious, IP unrelated, ongoing at final visit). See [Section 8.3.5](#) for reporting ongoing AEs at the end of protocol participation.

For SAEs that were incomplete or ongoing at the time of initial submission, the clinical site is required to submit follow-up SAE Report Forms when event information is available to the research site personnel and/or an outcome is known.

Investigators are not obligated to actively seek information on AEs or SAEs after conclusion of the study participation. However, if the investigator learns of any SAE, including a death, at any time after a participant has been discharged from the study, and he/she considers the event to be reasonably related to the study intervention or study participation, the investigator must promptly notify the sponsor.

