2. OVERVIEW OF STUDY DESIGN

Experimental Design:

This is a randomized, double-blind, placebo-controlled, pilot, Phase 2 exploratory study that will enroll subjects with a clinical diagnosis of COVID-19 confirmed by laboratory testing and who are in severe or critical condition as indicated by life-support measures.

Up to 60 subjects will be enrolled in the study. Eligible subjects will be randomized to either the CAP-1002 or placebo group (1:1 ratio) and undergo baseline safety and efficacy assessments approximately 1 to 5 days prior to the administration of investigational product (IP). Treatment administration consists of 1 peripheral intravenous (IV) infusions of IP [REDACTED] [REDACTED] for a total of 150M CDCs or matching placebo) administered at the clinical site.

Subjects will receive 1 administration of IP on study Day 1. Background standard of care treatment and practices will be maintained for all patients enrolled in the study.

[figure not shown]
There is no planned dose adjustment. Should an acute toxicity arise during the infusion (i.e., hypersensitivity reaction or pulmonary decompensation), the infusion should be terminated immediately, and the actual total dose administered recorded. Any decision about re-challenging should be made after discussions with the Investigator, Medical Monitor, and other medical experts who may be required to make an informed decision.

Subjects will complete Screening followed by a Treatment and Follow-up phase. A detailed medical history will be collected, including the presence of any co-morbidities and risk factors believed to be associated with COVID-19 outcomes (i.e., age, gender, diabetes, chronic obstructive pulmonary disease [COPD] or respiratory conditions, body mass index, cardiovascular or renal disease) or emergent factors since the time of infection. Screening and randomization will be conducted approximately 1 to 5 days prior to IP administration to allow enough time for IP delivery to the clinical site. Eligibility must be reviewed and confirmed on Day 1 prior to the infusion of IP. Follow-up will be conducted on Days 2, 3, 7, 15, 30, 60, and 90 either in the inpatient setting or by telephone if the subject has been discharged.

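### All-cause mortality has an open-ended cut-off but no scheduled contact after Day 90, so a single late reported death could collapse the Kaplan-Meier tail and create a spurious median

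*SAP*

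**What the plan says.** **Horizon.** SAP 11.1 gives the survival analysis no fixed length: "The final cutoff for the survival analysis will be as long as possible, and a calendar date for cutoff will be determined" before final unblinding. Deaths are taken from the Death Report dataset, and no time limit is stated.

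**Censoring.** The same section's rule begins: "For subjects not known to be deceased at time of analysis, the time between date of start of treatment and date of last contact". That interval, or the one ending when the subject was lost, is the censored time, capped at the data cut-off.

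**Contact.** SAP section 2 sets the visits: "Follow-up will be conducted on Days 2, 3, 7, 15, 30, 60, and 90 either in the inpatient setting or by telephone" for discharged subjects. The Day 90 window is ± 7 days, so the last scheduled contact is Day 97. Neither document schedules a vital-status check after that.

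**Late events.** Protocol 8.3.4 states: "Investigators are not obligated to actively seek information on AEs or SAEs after conclusion of the study participation". The duty to notify the sponsor applies "if the investigator learns of any SAE, including a death, at any time after a participant has been discharged from the study", and only where "he/she considers the event to be reasonably related to the study intervention or study participation".

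**Output.** SAP section 11 makes a Cox model, adjusted for a baseline risk score, the primary analysis. It adds unadjusted Kaplan-Meier curves, median survival with a 95% confidence interval, the number censored, and a log-rank test.

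**The concern.** Kaplan-Meier and Cox methods assume that whether a subject is still under observation is unrelated to the coming risk of death. Up to the Day 90 visit, scheduled contact supports that assumption. Beyond about Day 97, the documents provide no routine way for a living subject to stay in the risk set, but they do provide a route by which some deaths become known. A subject would then be counted as at risk after Day 97 mainly because a death was later reported. Survivors drop out of the denominator while reported deaths stay in.

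The route is also filtered by relatedness. Past Day 90, the deaths that must be newly reported are not all-cause, although the endpoint is.

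At stake are two reported results: the right-hand part of the survival curve and the median survival time. In a pilot of about 30 per arm meant to inform further studies, a false median is easy to misread.

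**Working it through.** The plan gives no mortality rate, event count or power for this endpoint, so there is no figure of its own to reproduce. I worked the rule through directly.

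**Inputs from the documents**
- About 30 subjects per arm (SAP section 4).
- Last contact between Day 83 and Day 97 (Day 90 ± 7).
- Censoring at last contact, open cut-off (SAP 11.1).
- Expected study duration 6 months (SAP section 2); final analysis after the last Day 90 visit and database lock (SAP 7.2). With the SAP's own conversion, 6 × 30.4375 = 182.6 days, so a subject treated at the very start could be about 182.6 − 90 ≈ 93 days past Day 90 by the end of the study.

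**Assumptions**
- 3, 6 or 9 deaths per arm by Day 60, and no loss to follow-up before Day 83.
- One late death reported on Day 120, or two on Days 120 and 150.

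**Kaplan-Meier.** S(t) is the product of (1 − d/r) over death times, with d deaths among r at risk. With 6 early deaths, S = 29/30 × 28/29 × … × 24/25 = 24/30 = 0.80. The other 23 survivors are censored by Day 97. On Day 120 one subject is at risk and dies, so S = 0.80 × (1 − 1/1) = 0. The median, the first time S is 0.5 or less, becomes Day 120 although 7 of 30 are known dead.

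| Early deaths of 30 | S at Day 90 | One late death: S, median | Two late deaths: S, median | One late death, all followed to Day 180: S, median |
|---|---|---|---|---|
| 3 | 0.90 | 0, Day 120 | 0.45 then 0, Day 120 | 26/30 = 0.867, not reached |
| 6 | 0.80 | 0, Day 120 | 0.40 then 0, Day 120 | 23/30 = 0.767, not reached |
| 9 | 0.70 | 0, Day 120 | 0.35 then 0, Day 120 | 20/30 = 0.667, not reached |

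The fall to 0 does not depend on early mortality. It needs only that every other subject in the arm was last contacted before the last late death. If k others were still under observation, S would instead be multiplied by k/(k + 1); with k = 5 and S = 0.80, the result is 0.80 × 5/6 = 0.667.

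**Log-rank.** Take 5 against 7 early deaths. Through Day 90, O − E = −1.105 and V = 2.971, so z = −1.105/√2.971 = −0.641 and p = 0.521.
- Late deaths in one arm only: everyone at risk is in that arm, so each late death adds 0 to O − E and 0 to V, and p stays at 0.521.
- One late death in each arm: at the first, one subject per arm is at risk, so E = 0.5 and V rises by 0.5 × 0.5 = 0.25 to 3.221. If the first is in the 5-death arm, O − E = −1.105 + 0.5 = −0.605 and p = 0.736. If it is in the other arm, O − E = −1.105 − 0.5 = −1.605 and p = 0.371.

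**Cox.** A death with one subject at risk contributes a factor of 1 to the partial likelihood. With two late deaths in the same arm, the treatment term cancels and only the risk-score covariate is informed.

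**How likely is a late reported death?** P(at least one in an arm) = 1 − (1 − (1 − m) × q × r)^30, where m is 90-day mortality, q is late mortality among survivors and r is the chance that a late death is reported. With m = 0.20, q = 0.05 and r = 0.30, this is 1 − 0.988^30 = 0.304. Over assumed ranges of m = 10–30% and q = 3–10%:

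| r | P(at least one) |
|---|---|
| 10% | 6–24% |
| 30% | 17–56% |
| 50% | 27–75% |

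**The case against.** Several stronger readings are tempting, and the documents do not support them.

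- **That the efficacy test is biased.** It is essentially untouched unless both arms have late reported deaths, as shown above. The curves and median are the unadjusted supplement to the Cox model.
- **That the distortion is certain.** It arises only if a death after Day 90 enters the Death Report before the cut-off. The likelihoods above rest wholly on assumed rates.
- **That vital status is never checked after Day 90.** Protocol 8.3.4 lifts an obligation to seek AEs and SAEs. It does not forbid collecting vital status, and a long cut-off may imply that the sponsor means to collect it. What can be said is that none is scheduled.
- **That only related deaths can appear.** Protocol 8.3.4 also requires follow-up forms for SAEs still open when first submitted, once an outcome is known. Whether that duty runs past Day 90 is unclear.
- **That a notified late death must be analysed as an event.** The protocol describes notification of the sponsor and does not say that this creates a Death Report record. The SAP sets no time limit that would exclude one, so inclusion is a reasonable but unconfirmed reading.

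Context also lowers the weight. The study is exploratory, p-values are descriptive, the number censored is reported, and the cut-off is set before unblinding. That last safeguard prevents choosing the date by result, but it does not make follow-up after Day 90 independent of outcome. An open horizon may be deliberate, since the endpoint list puts a 90-day limit on the duration endpoints and not on mortality. In that case the plan still lacks the common ascertainment that such a horizon needs.

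**Conclusion.** The point holds as a conditional defect in the descriptive survival output. The open cut-off, last-contact censoring and partial reporting of late deaths are all in the text. Together they allow one late reported death to take an arm's curve from 0.90, 0.80 or 0.70 to 0 and to produce a median where none has been reached. This assumes that every other subject in the arm was last contacted before that death and that the death reaches the Death Report before the cut-off. If no late death is recorded, there is no distortion. The documents do not support a claim that the treatment comparison is materially biased. The matter is worth settling before unblinding because the affected statistics will be reported and the remedy is small.

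**What to change.** In SAP 11.1, replace the open cut-off with a fixed horizon, for example: *Mortality will be analysed through Day 90. Subjects not known to have died by Day 90 will be censored at the earlier of last contact and Day 90; a subject known to be alive after Day 90, or who died after it, will be censored at Day 90. Deaths after Day 90 will be listed separately.* The words on the earlier date matter: censoring everyone at Day 90 would credit a subject lost at Day 40 with 50 days of survival that nobody observed. Day 90 matches the limit already set for the oxygen, ICU, hospital and adverse event endpoints.

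The cost is a short SAP edit. The small downside is that late deaths leave the model, though they stay in the listing.

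If a longer horizon is wanted, the alternative is to obtain vital status for every subject at a common cut-off. That keeps late deaths in the analysis but needs contact that neither document now schedules.
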